16.5 Sample analysis procedures

16.5.1 Ketone and lactate generation

Plasma samples will be analysed (for beta-hydroxybutyrate and lactate) by electron impact ionization, with selected ion monitoring for BOHB at m/z 233, and 237 for ¹³C4-BOHB.

16.5.2 Metabolomic analysis

Samples will be analysed for targeted and untargeted analyses using a combination of hydrophilic interaction liquid chromatography (HILIC) and Reverse Phase Ultra High-Performance Liquid Chromatography-mass spectrometry (UHPLC-MS) for polar and non-polar/lipid metabolites respectively.⁸⁶

Sample preparation for each targeted panel of metabolites (FFA, AA, energy metabolite/organic acids) will be performed following standardised SOPs. For untargeted analyses metabolites will be extracted from plasma using a dual phase Bligh-Dyer extraction as previously described.⁸⁶ Both targeted and untargeted panels will be analysed using a combination of hydrophilic interaction liquid chromatography (HILIC) and Reverse Phase Ultra High-Performance Liquid Chromatography-mass spectrometry (UHPLC-MS) for polar and non-polar/lipid metabolites respectively.⁸⁶

16.5.3 Whole blood leucocyte analysis

Whole blood will be collected into a tempus/PAxgene tube, and inverted and mixed with the preservative at the time of collection before freezing at -80°C. RNA extraction will occur at the central laboratory.

16.6 Sample and data recording/ reporting

Pseudonymised results will be shared on a password protected excel sheet with the CI and study team by secure electronic communication (email) after the last patient sample has been analysed.

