7.7 Mechanistic outcome measures

- Daily serum urea and creatinine concentrations, for the first 10 days after randomisation.
- Plasma metabolomic profiling at day one and day seven after randomisation.
- Ketone body generation at day one and day seven after randomisation.

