9.6 Unblinding

Blinding is critical to the integrity of the trial. However, it is understood that on rare occasions unblinding will be required (e.g., for medical or safety reasons if it will alter clinical management). For the purposes of this trial, if a patient experiences refractory acid-base abnormalities, hypo or hyperglycaemias, or vomiting that cannot be attributed to the clinical setting and causes concern to the responsible intensive care consultant (in regards to this affecting patient treatment or outcome), the intervention should be stopped. If this and/or conversion to standard feeding regimen does not resolve, unblinding may be required to change clinical management. The rescue treatment (being either cessation of the trial feed or conversion to a standard clinical feed) should not depend on the treatment group allocation, so unblinding requests are expected to be rare. Where unblinding is being considered, the PI (or assigned delegate) should have determined that the information is necessary, i.e., that it will alter the participant's immediate management. Site teams are encouraged to contact the study coordinating team if they wish to discuss this further, but they will always have the ability to unblind via the trial database.

Treatment identification information should be kept confidential and should be disseminated only to those individuals involved with the medical management of the participant. The CI will be kept informed of all instances of unblinding but should remain blinded to treatment allocations them self. The trial manager and the site staff will maintain a record of all unblinding events including patient trial ID, the date code break was performed, the person who broke the blind, and reason for it. The breaking of the code and the reasons for doing so will also be captured on the electronic case report form (eCRF), in the site file and medical notes. The code break for the trial will be held by the trial coordinator until the end of the trial when it will be filed in the Trial Master File (TMF). The CI will ensure any unblinding is documented at the end of the study in any final study report and/or statistical report. The information will also be disseminated to the Data Monitoring and Ethics Committee (DMEC) for review in accordance with the DMEC Charter.

9.7 30-Second Sit-To-Stand test (primary outcome)

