9.14 End of trial (EOT) definition

The EOT is defined as the date the last patient sample analysed. The CI is delegated the responsibility of submitting the EOT notification to REC once reviewed by sponsor. The EOT notification must be received by REC within 90 days of the end of the trial. If the study is ended prematurely, the CI will notify the Sponsor and REC, within 15 days, including the reasons for the premature termination.

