15.1 Data Management

Pseudonymised trial data will be transcribed onto the electronic CRF (eCRF) on the secure data entry web portal. All data will be pseudonymised at site, and a trial ID generated by the database. Age, patient initials and the trial ID will be used to identify the participants. The CRF will be designed by the database manager in the Critical Care and Perioperative Medicine Research group with input from the CI in accordance to Sponsor requirements. Only trial data related to the outcomes and data including safety events that will be used for statistical analysis will be collected. For participants that are withdrawn, data collected up to the point of withdrawal will be retained. Handling of withdrawal in terms of statistical analysis will be fully detailed in the statistical analysis plan.

Submitted data will be reviewed for completeness and consistency by authorised users within the trial coordinating team. Direct access to eCRF will be restricted, with only delegated and authorised users will be issued with (trial role related and defined) access to the eCRF. Each user will be assigned specific user roles and rights, and this will be reflected on the respective delegation log. Final sign-off by the site PI will be undertaken. Following data cleaning, a single final data lock will prevent changes to protect the final data set and will be exported from the study database for analysis by the trial statistician.

Storage and handling of confidential trial data and documents will be in accordance with the Data Protection Act 2018 (UK). A trial specific Data Management Plan will be developed by the coordinating team detailing all key methods of data management for collecting, recording, handling and storing of trial data. Transfer of patient identifiable information [contact] accounts and those used in [contact] will be secure and meet appropriate IT encryption and data protection requirements.

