16.2 Sample collection, labelling and logging

The following blood samples will be collected for all participants:

- 2x 6ml EDTA tubes will be collected for plasma separation for metabolomics and ketone body analysis at day one and day seven from point of randomisation.
- 1x 2.5ml whole blood will be collected for extra study specific bloods for leucocyte gene expression analysis at day 1 and day 7.
- 2x 10ml Whole blood will be collected for future study of immunological and metabolic assessments on days 1 and 7.

All blood samples will be pseudo-anonymised. Samples collected at each participating site will be labelled with the participant's corresponding trial ID and kept in a hospital freezer. The samples will be routinely collected and transferred to William Harvey Research Institute prior

to transfer to the different central laboratories by an approved courier company. The full sample, collection, labelling, logging and transfer procedure will be documented in the study laboratory log. The trial coordinating team will provide sites with a SOP on sample collection, processing and storage.

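### Laboratory results likely to indicate the arm may reach the CI and study team once the last sample is analysed, which can be before the last outcomes and before data lock

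*Protocol*

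**What the plan says.** Section 16.6 of the protocol shares pseudonymised laboratory results "with the CI and study team by secure electronic communication (email) after the last patient sample has been analysed". Section 9.14 uses the same event to close the trial: "The EOT is defined as the date the last patient sample analysed".

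The samples concerned are early ones. Section 7.7 lists "Ketone body generation at day one and day seven after randomisation" as a mechanistic outcome, and section 16.2 collects the plasma for it "at day one and day seven from point of randomisation". Samples are labelled with the trial ID (16.2), which is also one of the identifiers used for participants in the trial data (15.1).

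Outcomes run later: the 30-second sit-to-stand test, Barthel Index and PICUPS at day 30, and SF-36 and mortality at day 90 (7.4, 7.5). On closing the database, section 15.1 says: "Following data cleaning, a single final data lock will prevent changes to protect the final data set". Section 9.5 promises that research teams, patients and clinicians are blinded and gives no date at which this ends.

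**The concern.** The protocol does hold the laboratory results back, but ties the hold to completion of the assays. Neither completion of follow-up nor data lock is a condition. Pseudonymisation does not protect the blind, because the results carry the same trial ID as the outcome data. Section 5 reports that in the pilot ketosis was reached within 48 hours and sustained through the 10-day intervention, so a day-7 ketone value is likely to point to the arm for many participants.

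If the assays finish first, the CI and study team could infer allocation while the last outcomes are outstanding and while records are being queried. Some of what is settled before lock needs judgement. The intercurrent-event tables in section 7.8 have open categories for other events, including one for events that truncate the outcome, and two kinds of safety outcome in section 7.6 (acidosis and glucose episodes) turn on whether an event fits the clinical condition. A double-blind trial should not leave such decisions open to people who may know the arm.

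Separately, the end of trial as defined can be reached before the last participants have completed day-90 follow-up.

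**Working it through.** The protocol gives no figure to reproduce here. The check is the order of events, then the size of the possible overlap.

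**Order of events**

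| Event | Timing | Section |
|---|---|---|
| Last ketone and metabolomic sample | day 7 of the last participant | 7.7, 9.12, 16.2 |
| Last sample analysed: results shared, end of trial | day 7 plus assay turnaround (not stated) | 16.6, 9.14 |
| Last primary outcome | day 30 | 7.4 |
| Last SF-36 and mortality outcome | day 90 | 7.5 |
| Cleaning, then single lock | after the data are collected | 15.1 |

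Nothing in the protocol places the second row after any of the rows below it.

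**Largest gaps**, taking the last participant's day-7 sample as the last sample and assuming immediate analysis:

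- to the last day-30 outcome: 30 − 7 = 23 days
- to the last day-90 outcome: 90 − 7 = 83 days

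**Participants with outcomes open.** The number is 282 × gap ÷ recruitment length in days. The 282 is from section 12.2. Recruitment length is not stated (only a study duration of 48 months), so uniform recruitment over 18 to 42 months is assumed, with 30.44 days per month. These are upper bounds, at zero turnaround.

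| Recruitment (assumed) | Rate per day | Day-30 open (× 23) | Day-90 open (× 83) |
|---|---|---|---|
| 18 months | 282/547.9 = 0.515 | 11.8 (4.2%) | 42.7 (15.1%) |
| 24 months | 282/730.6 = 0.386 | 8.9 (3.1%) | 32.0 (11.4%) |
| 36 months | 282/1095.8 = 0.257 | 5.9 (2.1%) | 21.4 (7.6%) |
| 42 months | 282/1278.5 = 0.221 | 5.1 (1.8%) | 18.3 (6.5%) |

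Applying the 75% survival used for planning in section 12.1 to both time points leaves about 4 to 9 survivors with day 30 open and 14 to 32 with day 90 open.

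**Effect of turnaround** (assumed values):

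- 4 weeks: 28 days exceeds 23, so no day-30 outcome is open. For day 90, 83 − 28 = 55 days remain, giving 0.257 × 55 = 14.2 to 0.386 × 55 = 21.2 participants at 36 and 24 months of recruitment.
- 12 weeks: 84 days exceeds 83, so no day-90 outcome is open either.

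Beyond that point the remaining exposure is the cleaning of up to 282 records. It exists only if the assays end before lock.

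**The case against.** The best defence is that the hold in section 16.6 may work in practice. It prevents rolling release of ketone data during recruitment, and it sets an earliest time, not a duty to send at once. Samples are stored centrally, sent in batches and analysed at several laboratories (16, 16.1), so the authors may have expected the assays to finish last. A data management plan (15.1) or the statistical analysis plan might add a further hold. This stands as a limit on likelihood. It does not repair the text, which names the trigger and the recipients and lets release come before lock.

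Three stronger readings are tempting, and the protocol does not support them.

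- A reader might infer that the code list is released to the team at end of trial. Section 9.6 says only: "The code break for the trial will be held by the trial coordinator until the end of the trial when it will be filed". The place named for it is the TMF, and filing is not circulation.
- A reader might see a contradiction with the statement in section 9.6 that the CI "should remain blinded to treatment allocations them self". That sentence concerns individual code breaks and sets no general end to CI blinding. The promise at risk is the one in section 9.5.
- A reader might conclude that scoring of the primary outcome is biased. The recipients are not stated to include the site staff who count the stands, so this is not shown.

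It is also fair to say that ketone values will not identify the arm for everyone. The pilot statement is at group level, and trial feed can stop early once oral intake is established (10.1, 10.2.2).

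**Conclusion.** The point holds as a badly placed trigger, not as certain unblinding. Sections 16.6 and 9.14 allow results likely to indicate the arm to reach the CI and study team, and the trial to be declared ended, up to 23 days before the last day-30 outcome and up to 83 days before the last day-90 outcome, and before cleaning and lock.

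Under the assumed 18 to 42 months of recruitment, at most about 5 to 12 day-30 and 18 to 43 day-90 outcomes would be open. Both ranges fall with any laboratory delay and reach zero at about 3 weeks (23 days) and 12 weeks (83 days). The more lasting exposure is cleaning before lock, and that too vanishes if the assays finish after lock. The conclusion rests on the day-7 ketone result being informative about arm, which the pilot makes likely but the protocol does not quantify.

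**What to change.** Change three places in the next amendment.

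- **Section 16.6:** release participant-level ketone and metabolomic results to the CI and study team only after the clinical outcome data have been cleaned and locked. Until then the laboratories hold them, or a named role outside the blinded team does.
- **Section 15.1:** replace the single lock with two steps: lock of the clinical data, then lock and merge of the laboratory data. Without this, the ketone and metabolomic outcomes in section 7.7 would have no defined route into the analysis data set after the clinical lock.
- **Section 9.14:** define end of trial as the later of the last participant's day-90 follow-up and the last protocol-specified assay.

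The cost is small: a second lock to document, and a slightly later start to the mechanistic analyses and to the mediation analysis in section 12.1 that depends on them. No participant procedure, sample or outcome changes. With this wording no participant would have an outcome pending or an uncleaned clinical record when the laboratory results are released.

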16.7 Sample and data recording/ reporting

The samples will be stored beyond the end of the trial to be used for closely related studies in the future. After completion of any potential sub-studies the samples will be destroyed according to the Human Tissue Act Code of Practise.

16.8 Sample management at end of study

The samples will be stored beyond the end of the trial to be used for closely related studies in the future. After completion of any potential sub-studies the samples will be destroyed according to the Human Tissue Authority's Code of Practice. Consent will be obtained for the use of the leftover blood samples for closely related studies in the future.

17. Interventions and tools

17.1 Bioimpedance analysis

The Seca mBCA 525 (<https://uk.secashop.com/products/seca-mbca/seca-mbca-525/5250021009>) will be used for the bioimpedance analysis. Its use is contra-indicated in pregnancy and in patients with a permanent pacemaker. There are no additional risks attached to performing the analysis and the device is currently used in routine clinical care across hospitals in the UK.

17.2 Point of Care Ultrasound

Participating sites will use the ultrasounds machine that is available on the Critical Care Unit as part of standard of care.

17.3 Other biological or chemical products

Two ketogenic bespoke recipes will be used, depending on the clinical use of propofol infusions.

- 1) Ketogenic enteral feed with propofol: Fat 75% (MCT 47%), Carbohydrates 5% Protein 20%.
- 2) Ketogenic enteral feed without propofol: Fat 75% (MCT 75%), Carbohydrates 5%, Protein 20%.

Nestle Health Sciences will produce and package the control (equivalent in volume, energy and protein) in parallel for the control arm prior to site delivery, allowing a double-blind randomisation protocol to be used with maximal financial efficiency. Enteral feed packages will be colour and bar coded for randomisation, quality control and allocation purposes.

18. Safety Reporting

18.1 Adverse Events (AE)

An AE is any untoward medical occurrence in a subject to whom an intervention has been administered, including occurrences which are not necessarily caused by or related to that

intervention. An AE can therefore be any unfavourable and unintended sign, symptom or disease temporarily associated with study activities.

18.2 Adverse Reaction (ARs)

An AR is any untoward and unintended response in a participant to an intervention. All adverse events judged by either the reporting investigator or the sponsor as having a reasonable causal relationship to the intervention qualify as adverse reactions. The expression 'reasonable causal relationship' means in general that there is evidence or an argument to suggest a causal relationship.

18.3 Notification and reporting of AEs and ARs

The AE will be documented in the participants' medical records and the electronic Case Report Form (eCRF). The participant will be followed up by the research team until the AE is resolved.

The following safety events will be required for daily reporting from the point randomisation until day 10 and recorded in the eCRF. These events won't be reported as AEs:

- Acid-Base balance disruption, defined as unexpected acidosis not in keeping with the clinical condition, in the opinion of the treating clinician. The absence of documentation in the medical notes will be considered to indicate no concern.
- Hypoglycaemia episodes (normoglycaemia defined as 4.0-10.0 mmol/l), assessed from routine blood monitoring. Where no routine blood monitoring occurs, normoglycaemia is assumed.
- Hyperglycaemia episodes (normoglycaemia defined as 4.0-10.0 mmol/l) assessed from routine blood monitoring. Where no routine blood monitoring occurs, normoglycaemia is assumed.
- Diarrhoea defined as a Bristol School Score ≥ 5 .
- Vomiting defined as $>10\text{ml}$ of vomitus.
- Nausea defined as when an anti-emetic is given for patient-reported nausea.

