6.1 Summary of potential risks

Participants allocated to receiving the ketogenic feed could be susceptible to ketoacidosis if the ketones are not metabolised. This could exacerbate pre-existing systemic and cellular acidosis that carries a mortality risk to critically ill patients. There is a possibility that ketogenic diets can also minimise exogenous glucose delivery, predisposing patients to hypoglycaemia, which is harmful.³⁵ Lastly, ketogenic enteral feeds with a high lipid content could increase the risk of vomiting (and therefore pulmonary aspiration), and diarrhoea. However data from previously studies including our recently published trial (ASiCS) does not support concerns of acidosis, hypoglycaemia or vomiting, indicating that the feed is safe.^{34,37-45} It may be that ketogenic feeding reduces glucose variability and hypoglycaemia, decreasing harm to patients, an observation also seen in other ketogenic feeding trials in the critically ill.^{34,46,47} The signal for increased diarrhoea is unclear, as diarrhoea is extremely common in critically ill patients.³⁶

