7.6 Safety outcome measures

- New (post initiation of intervention) metabolic acidosis (Base Excess of >4 mEq/l) not in keeping with the clinical condition, in the opinion of the treating clinician within 10 days of randomisation.
- Hypoglycaemia episodes not in keeping with the clinical condition (normoglycaemia defined as 4.0-10.0 mmol/l), assessed from routine blood monitoring within 10 days from randomisation.

- Hyperglycaemia episodes not in keeping with the clinical condition (normoglycaemia defined as 4.0-10.0 mmol/l) assessed from routine blood monitoring within 10 days from randomisation.
- Days when an episode of diarrhoea (defined as a Bristol School Score ≥ 5) is recorded on nursing observation charts during the first 10 days from randomisation.
- Days where an episode of vomiting is recorded on nursing observation charts during the first 10 days from randomisation.
- Nausea defined as when an anti-emetic is given for patient-reported nausea assessed daily during the first 10 days from randomisation.

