9.5 Blinding

Our industry partner will use their existing packaging and logistical infrastructure to ensure bespoke colour packaging of the intervention and control feeds ensuring blinding is robust. Research teams, patients, and clinicians will be blinded to arm allocation.

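### The acidosis safety outcome has two conflicting definitions, and one of them codes silence in the notes as no event

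*Protocol*

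**What the plan says.** Section 6.1 opens its list of risks with this hazard: "Participants allocated to receiving the ketogenic feed could be susceptible to ketoacidosis if the ketones are not metabolised".

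Two later sections define the event meant to detect it.

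- Section 7.6 (safety outcome measures) counts new events of "metabolic acidosis (Base Excess of >4 mEq/l) not in keeping with the clinical condition, in the opinion of the treating clinician". The laboratory criterion and the opinion are both required, and the window is the first 10 days.
- Section 18.3 (reporting) describes "unexpected acidosis not in keeping with the clinical condition, in the opinion of the treating clinician". It gives no laboratory value and adds: "The absence of documentation in the medical notes will be considered to indicate no concern".

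Section 18.3 introduces its list with "The following safety events will be required for daily reporting from the point randomisation until day 10 and recorded in the eCRF", and then states "These events won't be reported as AEs". Under section 18.4 a serious adverse event is reported only if it is judged both related and unexpected. Section 9.5 says "Research teams, patients, and clinicians will be blinded to arm allocation".

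**The concern.** The two sections describe the same outcome but would not count the same events. Under section 18.3 a day on which a clinician considered acid-base status and was satisfied gets the same code as a day on which nobody looked. In patients with respiratory or multi-organ failure, a clinician blinded to feed can easily put a feed-related acidosis down to the illness and write nothing. With ordinary adverse event reporting closed for these events, little stands behind that judgement.

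The printed criterion in section 7.6 is a separate fault. A base excess above zero is a surplus of base, the opposite direction from metabolic acidosis, so the two halves of the definition do not describe one condition.

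Providing safety data is a secondary objective (section 7.2), and acid-base balance comes first among the pre-defined safety data in section 11.1. The point should not wait for the analysis plan, because these are data-capture rules. Section 15.1 limits collection to outcome and safety data that will be used in the analysis. If the eCRF follows section 18.3, the acid-base values may never be recorded, and no later analysis could recover them.

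**Working it through.** **Step 1. The two definitions side by side**

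| Element | Section 7.6 | Section 18.3 |
|---|---|---|
| Laboratory criterion | Base excess above 4 mEq/l, positive as printed | None |
| Clinician's opinion | Required | Required |
| New since the feed began | Required | Not stated |
| Rule for silent notes | None | Silence means no concern |

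Neither lets a laboratory value make an event by itself. Only section 18.3 turns missing documentation into a negative.

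**Step 2. Number per arm**

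Section 12.2 gives 282 in total. A two-sample t-test for a difference of 2, SD 4.06, 90% power and two-sided 5% needs 87.6 per arm, so 88, or 176 in total as stated. Then 176 / [(1 − 0.25 − 0.10) × 0.98²] = 176 / 0.6243 = 281.9, so 282. At 1:1 allocation this is 141 per arm. The safety set is defined by feed received (section 8.5), so 141 is approximate. The protocol states no acidosis rate, test or margin.

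**Step 3. Equal under-recording**

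Assumptions: true risks of 12% (ketogenic) and 4% (control), the same capture S in both arms, and no false positives. Observed risk = S × true risk.

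Power = Φ[(d − 1.96 × SE0) / SE1], where d is the observed difference, SE0 = √[2p̄(1 − p̄)/141] with p̄ the mean of the two observed risks, and SE1 = √[p1(1 − p1)/141 + p2(1 − p2)/141].

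- S = 1: (0.080 − 1.96 × 0.0323) / 0.0320 = 0.52, power 70%.
- S = 0.5: (0.040 − 1.96 × 0.0233) / 0.0232 = −0.25, power 40%.

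| Capture | Observed risks | Difference | Risk ratio | Power |
|---|---|---|---|---|
| 100% | 12% v 4% | 8 points | 3.0 | 70% |
| 75% | 9% v 3% | 6 points | 3.0 | 56% |
| 50% | 6% v 2% | 4 points | 3.0 | 40% |
| 25% | 3% v 1% | 2 points | 3.0 | 22% |

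The ratio is constant because S cancels. Its precision is not. The standard error of its logarithm is √[(1 − p1)/(141p1) + (1 − p2)/(141p2)], which is 0.47 at full capture and 0.68 at 50%. The 95% interval is therefore about 1.2 to 7.6 at full capture and 0.8 to 11.3 at 50%. Expected events at 50% capture are only about 8.5 and 2.8, so the normal approximation is rough there.

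Other assumed rates show the same pattern. From full to 40% capture, power goes from 67% to 31% for 10% v 3%, from 80% to 40% for 15% v 5%, and from 65% to 29% for 20% v 10%.

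**Step 4. Unequal under-recording**

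With true risks of 15% v 5% (ratio 3.0):

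- capture 0.5 ketogenic, 0.8 control: 7.5% v 4%, ratio 1.9;
- capture 0.8 ketogenic, 0.5 control: 12% v 2.5%, ratio 4.8.

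The direction is not fixed.

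**Step 5. What happens if every abnormal value counts**

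Assume illness-related acidosis with probability B in both arms, independent of the feed. Observed risk = 1 − (1 − p)(1 − B), with p = 12% and 4%.

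| Background B | Observed risks | Risk ratio | Power |
|---|---|---|---|
| 10% | 20.8% v 13.6% | 1.53 | 36% |
| 20% | 29.6% v 23.2% | 1.28 | 23% |
| 40% | 47.2% v 42.4% | 1.11 | 12% |

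A purely laboratory-based outcome can therefore lose as much power as heavy under-recording, and it also moves the ratio towards 1.

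**The case against.** A reader might infer that the comparison of acidosis between feeds is pulled towards no difference, whatever the measure. The documents do not support that. With equal capture the ratio does not move (step 3), and the protocol fixes no effect scale for this outcome. Blinding makes equal capture plausible but does not guarantee it, and unequal capture could err either way (step 4).

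A reader might also infer that the laboratory value should replace the clinician's judgement. Step 5 shows the price. In this population the attribution filter is a defensible way to remove background acidosis.

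Other safeguards exist. The eCRF asks for these events daily, beta-hydroxybutyrate and lactate are measured on days 1 and 7 (sections 9.12 and 16.5.1), refractory unexplained acid-base abnormality is addressed in section 9.6, and the DMEC reviews safety data. These lessen the risk of a missed signal, but none of them alters the event definition or separates an unassessed day from a normal one.

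It is also fair to say that the silence rule stands only in the reporting section, so applying it to the section 7.6 outcome is an inference. It is a natural one, since section 18.3 governs what enters the eCRF, but the need to infer it is itself a reason to reconcile the two. The printed sign may be a simple slip; it still needs correcting.

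**Conclusion.** The point holds in this form. Sections 7.6 and 18.3 define the acidosis outcome inconsistently, the base-excess criterion as printed does not fit the condition, and the silence rule codes unassessed or undocumented acidosis as a non-event. Followed as written, this lowers event counts, narrows the absolute difference in proportion to capture, and reduces the chance of detecting harm.

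The size is illustrative. At assumed true risks of 12% v 4% with 141 per arm, the difference halves from 8 to 4 points and power falls from about 70% to about 40% when half the events are captured. The rates and the capture proportion are assumptions, as are equal capture and the absence of false positives.

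It does not follow that the trial will wrongly report the feed as safe. The outcome is metabolic acidosis rather than ketoacidosis as such, the stated objective is to provide safety data, and no formal test rests on it.

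**What to change.** 1. Reconcile sections 7.6 and 18.3 into one definition, and correct the sign of the base-excess criterion. The sponsor should confirm the intended value; none is proposed here.
2. Record routine acid-base values in the daily eCRF whatever the clinician's opinion.
3. Hold the blinded clinician's attribution as a separate variable. Report the attributed outcome and the laboratory-based outcome side by side, neither replacing the other.
4. Delete the silence rule for acidosis. Code days without an assessment as not assessed, and report the number of assessed days by arm.

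The cost is a few eCRF fields taken from routine records and some redrafting. Background acidosis will dilute the laboratory-based comparison, which is why the attributed outcome stays. Some days will be missing, mostly after patients move to the ward, since the trial feed continues there and section 9.13 schedules no daily blood gas. That gap exists under the present rule too, where it is counted as no event.
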